Service provision assessments, at baseline, early and late intervention implementation, will assess: adherence to IMCI (or national guidelines) and device guidelines (during intervention phase), including proportion of: caregivers asked about all three danger signs; caregivers asked about all main symptoms; children with cough or difficulty breathing in whom a respiratory rate is counted for a minute and (where applicable) in whom a pulse oximetry reading is attempted, conducted correctly, obtained at first attempt or at repeated attempts; and proportion of children in whom CDSA is used and recommendations are adhered to. Furthermore, correctness of classification and treatment (as far as is possible with available information), and other indices of quality of care will be assessed. Facility and healthcare provider factors associated with health and quality of care impact and intervention uptake will be assessed.

Facility-based process maps and associated non-participant observational data will be described and compared between baseline and early and late intervention periods. Time (in minutes) will be compared (pre, early and late intervention) for total in clinic; in consultation; and on use of devices, and any other relevant single steps of the care process. Comparison will be made using mean (if parametric) or median (if non-parametric).

Qualitative enquiry with healthcare providers and caregivers will primarily focus on service provision, the participant response to the intervention and acceptability of devices, with exploration of change in perceptions, attitudes and behaviour over time. With caregivers, we will also explore experience of care and care-seeking behaviour through IDIs and walking interviews.

The sub-study of stakeholder perceptions, surveys and project data review will primarily focus on the processes, mechanisms and context (i.e. process evaluation criteria with focus on fidelity, dose, reach, context and adaptation) of implementation including adaptations made.

6.4.3 **Cost and modelled cost-effectiveness study**

- ξ Full implementation cost of the intervention per focal country (cost to health system as well as direct costs paid by the household to the health system)
- ξ Cost per child assessed using pulse oximetry devices and CDSA per country compared to without these supports.

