7.1.1 Quasi-experimental pre-post study

For each participant enrolled in the quasi-experimental pre-post study, data will be captured during the pre- and post-intervention periods according to the different assessments and Case Report Forms (CRFs) described in the visit schedule displayed in **Tab. 4**. A description of the variables collected in each CRF is available in the appendix.

Health facility visits

Quantitative research assistants will use an EDC mobile application to enter the research data of enrolled participants. The quantitative research assistant will collect from the caregiver screening information, information on care seeking behaviour, transport and costs, and clinical presentation and medical history. A number of in-depth sociodemographic and household variables will also be collected either as surrogate measures of household wealth, or known to be associated with health-seeking behaviour and / or child mortality (including maternal

education). Household wealth indicators were selected from DHS and other surveys in the study countries as those which best estimate wealth index that can be directly collected from the mother / caregiver and with a reasonable time vs. reliability trade-off. Data on laboratory investigations (if performed), final diagnosis, prescribed medication, referral or follow-up advice will be extracted from clinical notes and / or facility registers. Quantitative research assistants will seek clarification from healthcare providers only in cases where these variables are not clear from the records. Personally identifiable information (PII), including participant's name and date of birth, as well as caregiver's phone number and physical address, will be collected for linking data and detecting possible duplicates and carrying out the study follow-up.

During the post-intervention period, the research data of participants enrolled in the study will be linked with their CDSA consultation data. Additional information on oxygen saturation will be collected as recorded in clinical notes and / or facility registers. Pulse oximeter device savings will be cross-checked by quantitative research assistants at the end of the consultation where possible.

Follow-up

Quantitative research assistants will conduct the phone follow-up interviews using an EDC mobile application. Personally identifiable information (PII) will be used for contacting caregivers. A window of +3 days (Day 7 to Day 10) applies to Day 7.

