	
- Annualized¹ fixed/equipment costs (including pulse oximetry device and CDSA tablet costs)- Consumable costs (including medicines, diagnostic tests, and other consumables)- Personnel costs
3	Out of pocket costs
	
- Any out of pocket costs paid by patients' households to the health system to access care and prescribed treatment will be collected, including resources purchased outside the facility due to unavailability in the facility. However, care not prescribed by facility healthcare professionals will not be included.

1. Since costing needs to account for both capital and recurrent costs, annualizing capital costs (i.e. calculating the annual value of a capital item) is the easiest way of combining capital and recurrent costs meaningfully. Annualizing capital cost is based on three pieces of important information: the initial purchase price of the item, its expected useful life, and a discount rate

Sources of cost data

Personnel and procurement units of the organisations involved in the TIMCI intervention, especially through different local PATH offices and sampled facilities will be sourced for the cost data. Centrally available databases will be used to estimate personnel and consumable (including medicines and diagnostics) costs where available.

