	Consumables	Disposable items used per child per intervention	Quantity of consumables used per child	Medical personnel at health facility	Market prices	Centrally from government databases and complemented with provider's

						procurement department
	Equipment/ Capital (incurred every few years)	Pulse oximetry devices, tablets etc	Annualised cost of items	Interview, observations, and timing	Replacement prices	Provider's financial syndicate office
	Out of pocket costs	All out of pocket costs paid by patients' households to the health system for fever management	Direct fees and charges paid by households to health systems	Cost borne by households	Financial cost	Cost data collected from health system administrative records; information from interview of senior non- medical personnel

Definitions of types of costs and data to be collected

Staff time: For each activity within the TIMCI project, the responsible staff member involved with the activity will be identified. Secondly the time involved will be ascertained from the time-flow study and quantified. Supervision costs will similarly be estimated.

Consumables: The type and quantity of medicines, diagnostic tests and consumables used for each activity will be identified. In addition, unit costs of each consumable item will be obtained (for example the cost of an oxygen cylinder) and the size of unit (the time average spent on oxygen per patient).

Equipment: All equipment used for each activity will be identified and the price for which it was purchased. For the equipment costing, the lifespan for the equipment (usually between 3 – 5 years for smaller items including electronic tablets and pulse oximetry devices) will be obtained and annualized. Annualization will follow the cost recovery methodology where item cost, life span, and a defined interest rate is used to estimate the annual cost of an item. For equipment that is shared with other activities, the time spent per consultation will be obtained as a percentage of total time spent using each equipment and used to calculate the cost associated with the intervention after annualization. For donated equipment, market price information will be sought.

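### Protocol Tab. 7 confines out-of-pocket cost to fever management, against Tab. 6 and the any-illness population, and its named sources do not directly show prescribed items bought outside the facility

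*Protocol*

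**What the plan says.** Protocol 7.1.4 describes out-of-pocket cost in three places.

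- **Tab. 6 (cost centres):** "Any out of pocket costs paid by patients' households to the health system to access care and prescribed treatment will be collected". Items obtained elsewhere count as well, the definition being stated as "including resources purchased outside the facility due to unavailability in the facility". Care that facility staff did not prescribe is left out. No illness is singled out.
- **Tab. 7 (sources of cost data):** the category is what is paid by "households to the health system for fever management". The costing method is "Direct fees and charges paid by households to health systems". The valuation source is "Cost data collected from health system administrative records", together with an interview of senior non-medical personnel.
- **Text after Tab. 7:** household payments to health systems are to be estimated so that all health system costs are captured. Again there is no illness restriction.

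The outcome in Protocol 6.4.3 is full implementation cost per country: "cost to health system as well as direct costs paid by the household to the health system". It names no illness and does not mention outside purchases. Under Protocol 6.2.1 a child is eligible with any illness, apart from a consultation for trauma only.

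**The concern.** Tab. 7 is the table that tells costing staff what to identify, how to measure it and from whom. If its out-of-pocket row is narrower than the definition in Tab. 6, two teams could cost different things in good faith.

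Out-of-pocket payment is also the only household component of the costing, because Protocol 5.8 and 7.1.4 exclude caregiver time and transport. It enters full implementation cost and cost per child. Cost data are later combined with effectiveness data to give cost per DALY averted (Protocol 7.3.4).

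The intervention is not a fever intervention. Pulse oximetry is aimed at young infants, at children with cough or difficulty breathing (put at around 40-70% of primary care attendees in Protocol 6.3), and at those with moderate or severe signs. In Kenya it is recommended for all sick children under five. The antibiotic outcome covers every enrolled child. A fever-only row would therefore omit some of the household spending that the intervention may change.

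**Working it through.** The documents state no figure for out-of-pocket cost, so there is nothing to reproduce. The check compares the passages.

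**1. Scope by illness**

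| Place | Illness scope |
|---|---|
| Protocol 5.8, 6.4.3 | None stated |
| Protocol 6.2.1 (population) | Any illness, trauma-only excluded |
| Protocol 7.1.4, Tab. 6 | Any out-of-pocket cost for care and prescribed treatment |
| Protocol 7.1.4, Tab. 7 | Fever management |
| Protocol 7.1.4, text after Tab. 7 | All health system costs |

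The fever limit appears in one cell and nowhere else.

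**2. Effect of reading that cell literally**

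Protocol 7.3.4 derives unit cost as total cost divided by sample size. Let f be the share of true household spending that falls under fever management. A fever-only total divided by all children gives f times the true household cost per child, so the omitted share is 1 - f. The documents give no value of f. For illustration only:

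- f = 0.8 omits 1 - 0.8 = 20%.
- f = 0.4 omits 1 - 0.4 = 60%.

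The level of household cost per child can only be understated. The pre/post difference is another matter: it loses the change in non-fever spending, which can have either sign. If families buy fewer antibiotics for non-febrile children, leaving that saving out overstates incremental cost. If families pay more after referral of such children, leaving that out understates it.

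**3. Do the sources reach outside purchases?**

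- Fees and charges paid to health systems do not include a payment at an outside pharmacy, and neither facility records nor an administrator would normally hold that amount.
- The measurement-source cell of the row says only that the cost is borne by households. That describes who pays; it does not name an instrument.
- The costing respondents in Protocol 6.2.3, 6.6.3 and 9.3.3 are medical and non-medical personnel. Caregivers are not among them.
- Form TIMCI-04a (Protocol Tab. 4) does take costs from caregivers, and Protocol 7.1.1 lists "screening information, information on care seeking behaviour, transport and costs" among the items collected. But Protocol 6.5.1 places Day 0 caregiver data before the consultation except in emergencies, hence before that day's prescription is filled.
- TIMCI-04c is described as the patient journey at follow-up. The service provision assessment (SPA) exit interview is described in Protocol 7.1.3 as covering sociodemographic and clinical details and experience of care. Neither description mentions payments. The instruments are appended but not shown, so their items cannot be checked.

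**4. Outcome against cost centre**

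The outcome in 6.4.3 is limited to payments to the health system. A purchase from an outside pharmacy is not obviously such a payment. Outside purchases therefore enter only through Tab. 6, which itself combines them with payments to the health system. These two places also need to agree.

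**The case against.** A reader might infer that the plan restricts out-of-pocket cost to fever and that other household payments cannot be measured. The documents do not support that. The limit sits in one cell of a table introduced as listing broad areas, and every other statement on the topic is unrestricted. It may be leftover wording, though the documents cannot confirm this. Fee records and staff interviews are not shown to be fever-specific, and TIMCI-04a takes visit costs from caregivers of enrolled children whatever the illness.

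Nor are outside purchases beyond estimation. Protocol 7.1.4 takes volumes of prescribed tests and treatments from the time-flow and SPA studies, values consumables at market prices, and lets the costing use data collected elsewhere in the project. An imputed figure is feasible. What is missing is a stated rule and a stock-out share to drive it.

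A reader might also infer that hospital charges for non-febrile children are lost. They are not lost as such: referral and hospitalisation costs are sourced separately from personnel at referral facilities, with no fever limit. At most the part paid by households is affected.

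Finally, Protocol 5.8 calls the costing method not comprehensive and built on a most likely scenario, and 7.3.4 plans one-way sensitivity analysis. That limits the consequence. It does not settle which of two contradictory scopes applies, or where the outside purchases promised in Tab. 6 are to come from.

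**Conclusion.** The point holds as an unreconciled inconsistency plus a gap in sources. Tab. 7 contradicts Tab. 6, the text that follows it and the enrolled population on which illnesses count. Followed as written, it would understate household cost per child. Independently of that, the named sources do not directly capture prescribed items bought outside the facility.

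No size can be put on either part. The 20% and 60% above illustrate assumed values of f and are not estimates, and the direction for incremental cost is undetermined. The conclusion on understatement assumes that the Tab. 7 row is applied literally and divided by all children. The conclusion on sources rests on the instrument descriptions in the protocol, since the forms themselves are not available. The primary outcomes and the clinical comparison are untouched.

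**What to change.** 1. In Tab. 7, delete the words limiting the row to fever management, so that its scope is all sick-child consultations at 0-59 months.
2. For prescribed items bought outside the facility, choose one route and state it:
   - **Caregiver-reported amounts**, only if the existing instruments collected them both before and after the intervention.
   - **Imputation:** prescribed volume (SPA and time-flow studies) x market price x assumed stock-out share, with the stock-out share varied in the one-way sensitivity analysis already planned.
   - **A narrower outcome:** fees paid to the health system, which agrees with Protocol 6.4.3. Amend Tab. 6 to match and report that outside purchases are excluded.

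Adding a caregiver question now would not repair the comparison. The Protocol summary anticipated that data collection would end in Q1 2023, and the SAP is dated 05/04/2023 and describes training in the past tense. A new item could at best yield post-intervention data with no baseline.

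The cost is a table edit plus either a little more costing analysis or a narrower stated outcome. As a protocol modification, it would go to the ethics committees and registries if judged important (Protocol 9.2).

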7.2 Data management

All data management procedures will be further described in the Data Management Plan (DMP).

7.2.1 Data flow, storage and transfer

The data management system will process and combine two main data flows: the research data flow, which will be managed by a secure third-party cloud based EDC platform, and the routine consultation data flow, which will be managed by a customized PostGreSQL Server (Unisanté/Wavemind, Lausanne, Switzerland). As illustrated in **Fig. 7**, there will be separate secured databases with restricted access rights for storing and processing CDSA consultation data, research data for each study, PII that are necessary for all research operations, and (possible) linking between the different databases.

- ξ **Study databases** – These databases will contain de-identified quantitative research data collected in study facilities. Unless specified otherwise per country requirements in the DMP, these databases will be hosted on a device owned and maintained by the country research partner.
- ξ **CDSA consultation database** – This database will contain routine consultation data extracted from CDSA in all intervention facilities. CDSA consultation data from study facilities will be de-identified, i.e. a link will exist between these data, the pre-post study database and the identification database. There will be no such link for CDSA consultation data from non-study facilities, which will then be fully anonymised. Unless specified otherwise per country requirements in the DMP, this database will be hosted on a device owned and maintained by the country research partner.
- ξ **Identification database** – This database will contain PII collected in study facilities. It will be kept under strict operating procedures, in particular it will not be shared or accessible outside of the country. The database will be used for generating follow-up call logs and random selection of a purposive sample of caregivers for qualitative studies. It will also be used for flagging possible duplicates in children enrolled in the pre-post study.

§ **Mapping database** – This database will be used for linking data from the study databases and the identification database. Each table will be maintained confidential under strict operating procedures for the duration of the study. The mapping between databases will not be shared or accessible outside of the research institution. When all data validation and regulatory requirements have been met, the mapping database will be destroyed, so that all the study databases and CDSA consultation database are ultimately fully anonymized and independent from each other.

In addition, **qualitative study repositories** with restricted access rights will store raw (audio-recordings, notes, drawings, photos, videos, GPS coordinates and document review grids) and processed (transcribed, translated and coded) labelled qualitative material. Unless specified otherwise per country requirements in the DMP, these repositories will be hosted on a device owned and maintained by the country research partner.

A data transfer agreement will be requested from the national competent authorities for providing access to and sharing a full copy of the de-identified study databases, de-identified consultation database and de-identified qualitative material with the core team at Swiss TPH. A subset of these database will be additionally shared with UoW as needed for the cost and cost-effectiveness study. Following approval from the national competent authorities, the copies will be stored on servers hosted in Switzerland / Canada. Data ownership will remain with the country research partner. After study termination or premature termination of the study, the de-identified databases and de-identified qualitative material will be archived by the country research partner in accordance with national laws. The shared copies will be archived for 10 years by Swiss TPH and UoW, unless otherwise stipulated by the applicable legislation. Research partners will archive study data according to the applicable national regulations. After the mandatory retention period has ended, a periodic review will check if data storage is still needed for research purposes. If not, the study data will then be deleted. All repositories, databases and related software files will be backed up by the administrator in conjunction with any updates or changes.

[figure not shown]

Fig. 7. Overview of the research data and consultation data flows and supporting IT architecture used within the TIMCI project. MedAL-R can receive updates directly from MedAL-C to be able to deploy patches as needed. The MedAL-C server is hosted in Switzerland and managed by the IT Unisanté team in Lausanne. This server will receive connection logs from the tablets when a network access is available.

7.2.2 Data entry, handling and validation

Quantitative research data

The EDC mobile application will perform offline validation (e.g., range and consistency) checks that immediately detect and request the correction of erroneous data entry, and prevent missing values upon compulsory data entry, guaranteeing completeness of the mandatory datasets. Standardized dictionaries such as SNOMED CT and ICD-10 will be implemented within the data collection tools (and hence available offline) in order to code clinical findings and symptoms in a consistent way. To ensure the integrity of the study-related duties and any data generated, each quantitative research assistant will log into the EDC mobile application using their secure user name and password. All passwords will be strictly personal and confidential. Electronically signed data from the mobile application will be regularly synchronized with the central server.

Procedures for cleaning and coding quantitative data will be developed by the core data manager at Swiss TPH to ensure consistency across countries. These procedures will be further described in the Data Management Plan. Data cleaning and coding activities will be supervised by the data manager in charge in each country, with possible country-specific additions. These activities will include, but will not be limited to, data de-identification, duplicate management and free text management. Data quality checks will be run on a daily basis. A follow-up log based on baseline visits and referral facility log based on Day 7 phone follow-up outputs will be generated daily. The server will certify the integrity of data by using in-built range and consistency checks to prevent errors during data manipulation.

An audit trail will be maintained for the life of the study for all quantitative research data. If a correction is required for an entry, the time and date stamps will track the person entering or updating entry and creates an electronic audit trail. There will be access control on the audit trails so that a user cannot view information about another user or site that they are not allowed to see. A synthetic visualization of the audit trail will be readily accessible by the data manager in charge in each country, so that they can check all modification to data and meta-data and who made them, as well as all successful and attempted system logins. At critical junctures of the pre-post study, the research database will be reviewed and cleaned per established procedures, before being locked. Consistency between the data cleaning procedures in each country will be regularly reviewed. In addition, a dashboard will be developed for facilitating the review of key indicators to trigger in-depth data review.

CDSA individual consultation data

Each patient attending an intervention facility will be given a unique identifier in the CDSA used by this facility. Each new visit at the same facility will create a new case for the patient. Similar to EDC mobile application, MedAL-R will perform offline validation checks and relies on standardized dictionaries code clinical findings and symptoms in a consistent way. MedAL-R will allow the modification of consultation data by different healthcare providers within the health facility until the case has been closed to ensure the flexibility required by the clinical workflow. Routine consultation data from MedAL-R will be regularly synchronized with the CDSA server. Consultation data records will be electronically signed before being transferred to the central research database. A timestamp (date, time, device identifier number) will guarantee the integrity of the data associated with the electronic signature.

In non-study facilities, CDSA consultation data will be anonymised before transfer, so that no PII will leave the facility and these data can never be re-associated with the underlying individual.

Qualitative research data

Qualitative data will be voice recorded and complemented by written notes, drawings, photos and videos and GPS coordinates by a dedicated qualitative researcher. Audio-recordings, notes, drawings, photos, videos, GPS coordinates and document review grids will be either written up in electronic files and/or directly transferred to the qualitative researcher's computer

and uploaded to the central server. Electronic files will be stored on two separate password-protected devices according to country specific mechanisms (e.g. audio recording stored on a password protected computer and on an external drive in a password protected folder in locations where internet cannot be accessed; back-up on server as soon as internet is available and deleting from external drive).

Qualitative research data will be backed up at the first possible opportunity. Where connectivity to the central server is not possible, field teams will make a second back up on an encrypted external hard drive. Transcription and translations from voice recordings and hand-written notes will be entered into Word documents and translated into English and/or French. Hand-drawn process maps and health care seeking pathways will be digitalized.

